9.4.2 Safety Data

Safety data will be summarized for the Safety Analysis Population. Subjects receiving a vaccination according to a study arm other than the study arm to which they were randomized, will be analyzed according to the vaccination(s) they actually received. Safety summaries will be presented for each dose group by presence or absence of ALFQ.

The proportion of subjects reporting at least one solicited AE will be summarized for each solicited AE, any systemic symptom, any local symptom, and any symptom. The 95% CI will be presented, and a Fisher's exact test will be performed to test for differences in the proportion of subjects reporting a solicited AE within dose groups between those with and without adjuvant.

Solicited AEs will be summarized by maximum severity for each day after each study vaccination for Days 1-8. The number, percentage (observed rate), and exact two-sided 95% CI for subjects reporting each solicited AE within 8 days following vaccination will be summarized. In addition, maximum severity for each solicited AE will be determined for each subject and reported by study arm and the resulting number and percentage of subjects will be summarized by severity grade (none, mild, moderate, severe). Summaries of solicited AEs will be presented separately by study arm for each study vaccination as well as overall study vaccinations.

Vaccine-related unsolicited AEs will be coded by MedDRA® for preferred term and system organ class (SOC). The number of SAEs, MAAEs, NOCMCs, and PIMMCs are likely to be small in this trial and will be reported by detailed listings showing the event description, MedDRA® preferred term and SOC, relevant dates (study vaccinations and AE duration), severity, relatedness, and outcome. If the number of events permits, a Fisher's exact test may be used to test for differences in unsolicited AE rates between adjuvant and non-adjuvant groups within dose levels, in a similar manner as for solicited AEs.

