  - Unexpected event means an event unforeseen by the researcher or the participant, in terms of nature, severity, or frequency, and is not listed in the Investigator's Brochure, package insert, and/or summary of product characteristics.
- At least possibly related to the study product.

NOCMCs are defined as any new ICD-10 diagnosis that is applied to the participant during the duration of the study, after receipt of the study agent, that is expected to continue for at least 3 months and requires continued health care intervention.

MAAEs are any unsolicited AE for which a participant received medical attention, defined as hospitalization, an ER visit, or an otherwise unscheduled visit to or from medical personnel.

PIMMCs constitute a group of AEs that includes diseases which are clearly autoimmune in etiology and other inflammatory and/or neurologic disorders which may or may not have autoimmune etiologies. A list of qualifying conditions is in Appendix C of the protocol [v6.0, 08MAY2023].

Any medical condition that is present at the time that the participant is screened will be considered as baseline and not reported as an AE. However, if the severity of any pre-existing medical condition increases, it should be recorded as an AE.

Solicited adverse events are AEs that are common and known or expected to occur following the administration of the study product. Participants will be assessed for solicited AEs prior to and 30 minutes after each vaccine administration prior to the participant leaving the clinic. On the day of vaccination, participants will receive a thermometer and instructions to complete an e-memory aid to record symptoms for 7 days following each vaccination. The participant e-memory aid will be reviewed with the participant at study visits 48 hours and 7 days after each vaccination (Study Visits 02, 03, 06, 07, 10, and 11). Any symptoms still present after the solicited event collection period (Study Days 1-8 for first vaccination, Study Days 29-36 for second vaccination, and Study Days 57-64 for third vaccination) will continue to be followed until resolution or determined to be stable per investigator. Solicited events will be graded using the Toxicity Grading Scales in [Table 5](#); for quantitative measurements of local injection site reactions, the grading scale classifications of "Small", "Medium", and "Large" will be presented as "Mild", "Moderate", and "Severe" respectively for consistency with other AEs.

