- Solicited (local injection site) events listed for this protocol include qualitative measurements of pain, tenderness, ecchymosis, erythema, and induration/edema and quantitative measurements of ecchymosis, erythema, and induration/edema.
- Solicited (systemic) events listed in this protocol include fever (elevated oral temperature), feverishness, fatigue, malaise, myalgia, arthralgia, headache, nausea, and vomiting.

Unsolicited adverse events will be collected starting after the first vaccination through 28 Days after the last vaccination. SAEs, MAAEs, NOCMCs, and PIMMCs will be collected starting after the first vaccination through the final study visit.

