### 9.3.1.     Solicited Events and Symptoms

Temperatures collected on the Vital Signs eCRF within 7 days following vaccination will be considered towards the solicited AE of fever and will be included in all tables, figures, and listings summarizing solicited AEs.

The number and percentage with 95% CI of participants reporting at least one solicited adverse event of at least mild severity within 7 days following vaccination will be summarized for each solicited symptom, any systemic symptom, any local symptom, and any symptom following each vaccination and following any vaccination for Cohort 1 ([Table 32](#)), Cohort 2 ([Table 33](#)), and Cohort 3 ([Table 34](#)). The 95% CI will be calculated using Clopper-Pearson methodology from a binomial distribution (SAS Proc Freq with a binomial option).

For each systemic and local symptom, any systemic symptom, any local symptom, and any solicited symptom, the number and percentage of participants reporting the symptom will be summarized by severity for each day and maximum severity within 7 days after each vaccination for Cohort 1 for vaccination 1 ([Table 35](#)), vaccination 2 ([Table 36](#)), vaccination 3 ([Table 37](#)), and any vaccination ([Table 38](#)). Analogous tables for each vaccination and any vaccination will be presented for Cohort 2 ([Table 39](#), [Table 40](#), [Table 41](#), and [Table 42](#)) and Cohort 3 ([Table 43](#), [Table 44](#), [Table 45](#), and [Table 46](#)). For each event the denominator is the number of participants with non-missing data for the specific event.

The percentage of participants reporting any solicited systemic symptom will be summarized graphically in a bar chart by maximum severity, day post vaccination, and vaccination group for each vaccination ([Figure 32](#), [Figure 33](#), and [Figure 34](#)) and for all vaccinations combined ([Figure 35](#)). Analogous figures will be presented for any solicited local symptom ([Figure 36](#), [Figure 37](#), [Figure 38](#), and [Figure 39](#)).

The percentage of participants experiencing each solicited symptom within 7 days of vaccination will be summarized in a bar chart by maximum severity and treatment group for each vaccination ([Figure 40](#), [Figure 41](#), and [Figure 42](#)) and for all vaccinations combined ([Figure 43](#)).

All solicited adverse events will be presented by participant in [Listing 9](#) for systemic symptoms and [Listing 10](#) for local symptoms.

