## 14.3 Safety Data

### 14.3.1 Displays of Adverse Events

**Table 30: Overall Summary of Adverse Events**

*[Implementation Note: For the severity rows, a participant will only be counted in one severity category and will be categorized by the maximum severity experienced.]*

	1 µg CJCV2 (N=X)		1 µg CJCV2+ALFQ (N=X)		3 µg CJCV2 (N=X)		3 µg CJCV2+ALFQ (N=X)		10 µg CJCV2 (N=X)		10 µg CJCV2+ALFQ (N=X)		All Participants (N=X)	
Participants with	n	%	n	%	n	%	n	%	n	%	n	%	n	%
At least one local solicited adverse event a	x	x	x	x	x	x	x	x	x	x	x	x	x	x
At least one systemic solicited adverse event a	x	x	x	x	x	x	x	x	x	x	x	x	x	x
At least one unsolicited adverse event b	x	x	x	x	x	x	x	x	x	x	x	x	x	x
Mild (Grade 1)	x	x	x	x	x	x	x	x	x	x	x	x	x	x
Moderate (Grade 2)	x	x	x	x	x	x	x	x	x	x	x	x	x	x
Severe (Grade 3)	x	x	x	x	x	x	x	x	x	x	x	x	x	x
At least one related unsolicited adverse event b	x	x	x	x	x	x	x	x	x	x	x	x	x	x
Mild (Grade 1)	x	x	x	x	x	x	x	x	x	x	x	x	x	x
Moderate (Grade 2)	x	x	x	x	x	x	x	x	x	x	x	x	x	x
Severe (Grade 3)	x	x	x	x	x	x	x	x	x	x	x	x	x	x
At least one clinical laboratory adverse event a	x	x	x	x	x	x	x	x	x	x	x	x	x	x
At least one related clinical laboratory adverse event a	x	x	x	x	x	x	x	x	x	x	x	x	x	x
At least one serious adverse event c,d	x	x	x	x	x	x	x	x	x	x	x	x	x	x

	1 µg CJCV2 (N=X)		1 µg CJCV2+ALFQ (N=X)		3 µg CJCV2 (N=X)		3 µg CJCV2+ALFQ (N=X)		10 µg CJCV2 (N=X)		10 µg CJCV2+ALFQ (N=X)		All Participants (N=X)	
Participants with	n	%	n	%	n	%	n	%	n	%	n	%	n	%
At least one related, serious adverse event c,d	x	x	x	x	x	x	x	x	x	x	x	x	x	x
At least one adverse event leading to early termination e	x	x	x	x	x	x	x	x	x	x	x	x	x	x
At least one medically attended adverse event d	x	x	x	x	x	x	x	x	x	x	x	x	x	x
At least one new onset chronic medical condition d	x	x	x	x	x	x	x	x	x	x	x	x	x	x
At least one potentially immune mediated medical condition d	x	x	x	x	x	x	x	x	x	x	x	x	x	x

Notes: N = Number of participants in the Safety Population.

Participants can only be counted once for each category regardless of the number of events and are categorized by maximum severity.

a Collected from vaccination through 7 days post vaccination for each vaccination.

b Collected from vaccination through 28 days post vaccination for each vaccination.

c A listing of Serious Adverse Events is included in Section 14.3.2.

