	Day 6	x	xx	x	xx	x	xx	x	xx	x	xx	x	xx	x	xx	x	xx
	Day 7	x	xx	x	xx	x	xx	x	xx	x	xx	x	xx	x	xx	x	xx
	Day 8	x	xx	x	xx	x	xx	x	xx	x	xx	x	xx	x	xx	x	xx
	Maximum	x	xx	x	xx	x	xx	x	xx	x	xx	x	xx	x	xx	x	xx
Local Symptoms	Pre-Vac	x	xx	x	xx	x	xx	x	xx	x	xx	x	xx	x	xx	x	xx
	Post Vac	x	xx	x	xx	x	xx	x	xx	x	xx	x	xx	x	xx	x	xx
	Day 1	x	xx	x	xx	x	xx	x	xx	x	xx	x	xx	x	xx	x	xx
	Day 2	x	xx	x	xx	x	xx	x	xx	x	xx	x	xx	x	xx	x	xx
	Day 3	x	xx	x	xx	x	xx	x	xx	x	xx	x	xx	x	xx	x	xx
	Day 4	x	xx	x	xx	x	xx	x	xx	x	xx	x	xx	x	xx	x	xx
	Day 5	x	xx	x	xx	x	xx	x	xx	x	xx	x	xx	x	xx	x	xx
	Day 6	x	xx	x	xx	x	xx	x	xx	x	xx	x	xx	x	xx	x	xx
	Day 7	x	xx	x	xx	x	xx	x	xx	x	xx	x	xx	x	xx	x	xx
	Day 8	x	xx	x	xx	x	xx	x	xx	x	xx	x	xx	x	xx	x	xx
	Maximum	x	xx	x	xx	x	xx	x	xx	x	xx	x	xx	x	xx	x	xx
Ecchymosis																	
	Post Vac	x	xx	x	xx	x	xx	x	xx	x	xx	x	xx	x	xx	x	xx
	Day 1	x	xx	x	xx	x	xx	x	xx	x	xx	x	xx	x	xx	x	xx
	Day 2	x	xx	x	xx	x	xx	x	xx	x	xx	x	xx	x	xx	x	xx
	Day 3	x	xx	x	xx	x	xx	x	xx	x	xx	x	xx	x	xx	x	xx

Symptom	Day Relative to Vaccination	1 ug CJC2V (N=X)								1 ug CJC2V+ALFQ (N=X)							
		None		Mild		Moderate		Severe		None		Mild		Moderate		Severe	
		n	%	n	%	n	%	n	%	n	%	n	%	n	%	n	%
	Day 4	x	xx	x	xx	x	xx	x	xx	x	xx	x	xx	x	xx	x	xx
	Day 5	x	xx	x	xx	x	xx	x	xx	x	xx	x	xx	x	xx	x	xx
	Day 6	x	xx	x	xx	x	xx	x	xx	x	xx	x	xx	x	xx	x	xx
	Day 7	x	xx	x	xx	x	xx	x	xx	x	xx	x	xx	x	xx	x	xx
	Day 8	x	xx	x	xx	x	xx	x	xx	x	xx	x	xx	x	xx	x	xx
	Maximum	x	xx	x	xx	x	xx	x	xx	x	xx	x	xx	x	xx	x	xx
Ecchymosis (measurement)	Post Vac	x	xx	x	xx	x	xx	x	xx	x	xx	x	xx	x	xx	x	xx
	Day 1	x	xx	x	xx	x	xx	x	xx	x	xx	x	xx	x	xx	x	xx
	Day 2	x	xx	x	xx	x	xx	x	xx	x	xx	x	xx	x	xx	x	xx
	Day 3	x	xx	x	xx	x	xx	x	xx	x	xx	x	xx	x	xx	x	xx
	Day 4	x	xx	x	xx	x	xx	x	xx	x	xx	x	xx	x	xx	x	xx
	Day 5	x	xx	x	xx	x	xx	x	xx	x	xx	x	xx	x	xx	x	xx
	Day 6	x	xx	x	xx	x	xx	x	xx	x	xx	x	xx	x	xx	x	xx
	Day 7	x	xx	x	xx	x	xx	x	xx	x	xx	x	xx	x	xx	x	xx
	Day 8	x	xx	x	xx	x	xx	x	xx	x	xx	x	xx	x	xx	x	xx
	Maximum	x	xx	x	xx	x	xx	x	xx	x	xx	x	xx	x	xx	x	xx
Erythema	Post Vac	x	xx	x	xx	x	xx	x	xx	x	xx	x	xx	x	xx	x	xx
	Day 1	x	xx	x	xx	x	xx	x	xx	x	xx	x	xx	x	xx	x	xx
	Day 2	x	xx	x	xx	x	xx	x	xx	x	xx	x	xx	x	xx	x	xx
	Day 3	x	xx	x	xx	x	xx	x	xx	x	xx	x	xx	x	xx	x	xx
	Day 4	x	xx	x	xx	x	xx	x	xx	x	xx	x	xx	x	xx	x	xx
	Day 5	x	xx	x	xx	x	xx	x	xx	x	xx	x	xx	x	xx	x	xx

Symptom	Day Relative to Vaccination	1 ug CJC2V (N=X)								1 ug CJC2V+ALFQ (N=X)							
		None		Mild		Moderate		Severe		None		Mild		Moderate		Severe	
		n	%	n	%	n	%	n	%	n	%	n	%	n	%	n	%
	Day 6	x	xx	x	xx	x	xx	x	xx	x	xx	x	xx	x	xx	x	xx
	Day 7	x	xx	x	xx	x	xx	x	xx	x	xx	x	xx	x	xx	x	xx

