	Day 1	x	xx	x	xx	x	xx	x	xx	x	xx	x	xx	x	xx	x	xx
	Day 2	x	xx	x	xx	x	xx	x	xx	x	xx	x	xx	x	xx	x	xx
	Day 3	x	xx	x	xx	x	xx	x	xx	x	xx	x	xx	x	xx	x	xx
	Day 4	x	xx	x	xx	x	xx	x	xx	x	xx	x	xx	x	xx	x	xx
	Day 5	x	xx	x	xx	x	xx	x	xx	x	xx	x	xx	x	xx	x	xx
	Day 6	x	xx	x	xx	x	xx	x	xx	x	xx	x	xx	x	xx	x	xx
	Day 7	x	xx	x	xx	x	xx	x	xx	x	xx	x	xx	x	xx	x	xx
	Day 8	x	xx	x	xx	x	xx	x	xx	x	xx	x	xx	x	xx	x	xx
	Maximum	x	xx	x	xx	x	xx	x	xx	x	xx	x	xx	x	xx	x	xx

Notes: N = Number of participants in the Safety Population who received the specified vaccination; Vac = Vaccination.

“Pre-Vac” is the assessment prior to vaccination (systemic symptoms only), “Post Vac” is the in-clinic assessment 30 minutes after vaccination; “Day 1” is from the memory aid completed by the participant for the day of vaccination; “Maximum” is the maximum severity reported within 7 days following vaccination.

aFever was only collected for reactogenicity on the memory aid.

bChills/shivering/sweating.

Tables with similar format:

**Table 36: Number and Percentage of Participants Experiencing Solicited Events by Symptom, Severity, Day Relative to Vaccination, and Treatment Group – Cohort 1, Vaccination 2**

**Table 37: Number and Percentage of Participants Experiencing Solicited Events by Symptom, Severity, Day Relative to Vaccination, and Treatment Group – Cohort 1, Vaccination 3**

**Table 38: Number and Percentage of Participants Experiencing Solicited Events by Symptom, Severity, Day Relative to Vaccination, and Treatment Group – Cohort 1, Any Vaccination**

**Table 39: Number and Percentage of Participants Experiencing Solicited Events by Symptom, Severity, Day Relative to Vaccination, and Treatment Group – Cohort 2, Vaccination 1**

---

**Table 40:** Number and Percentage of Participants Experiencing Solicited Events by Symptom, Severity, Day Relative to Vaccination, and Treatment Group – Cohort 2, Vaccination 2

**Table 41:** Number and Percentage of Participants Experiencing Solicited Events by Symptom, Severity, Day Relative to Vaccination, and Treatment Group – Cohort 2, Vaccination 3

**Table 42:** Number and Percentage of Participants Experiencing Solicited Events by Symptom, Severity, Day Relative to Vaccination, and Treatment Group – Cohort 2, Any Vaccination

**Table 43:** Number and Percentage of Participants Experiencing Solicited Events by Symptom, Severity, Day Relative to Vaccination, and Treatment Group – Cohort 3, Vaccination 1

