**Listing 10: Solicited Events – Local Symptoms**

*[Implementation Note: In the “Vaccination Number (Study Day)” column, display the vaccination number followed by the actual study day the vaccination was received in parentheses, e.g., “Vac 1 (Day 1)”. The “Severity” column for quantitative measurements should include the measurement in parentheses after the result, e.g., “Mild (3 mm)”. For the “Day Relative to Vaccination” column, “Post Vac” is the assessment 30 minutes after vaccination, and “Day 1” is the maximum over the remainder of the day of vaccination. The “Day Relative to Vaccination Symptom Resolved” column will be relative to the associated vaccination where the day of the associated vaccination is Day 1. For events ongoing past Day 8, the “Vaccination Number (Study Day)” and “Day Relative to Vaccination” columns should include the days of start (Day 9) and end, e.g., (Day 9 – Day 12); the “Severity” column will be the maximum severity (and measurement if applicable) during that time period. Include all solicited events from the Treatment Administration Record and Solicited Events eCRFs. In the CSR, Participant ID should be USUBJID (not PATID) for purposes of de-identification. Sort by Treatment Group, Participant ID, Vaccination Number, Day Relative to Vaccination, and Symptom. Note that the values in the table are meant to represent possible values expected for that column and are not necessarily associated with entries in other columns in the same row.]*

Treatment Group	Participant ID	Vaccination Number (Study Day)	Day Relative to Vaccination	Assessment a	Symptom	Severity
1 µg CJCV2	EHD.XXXXX	Vac 1 (Day 1)	Post Vac	MA	Ecchymosis	None
1 µg CJCV2+ALFQ		Vac 1 (Day 1)	Day 1	Clinic	Ecchymosis (measurement)	Mild
3 µg CJCV2		Vac 1 (Day 2)	Day 2		Erythema	Moderate
3 µg CJCV2+ALFQ		Vac 1 (Day 3)	Day 3		Erythema (measurement)	Severe
10 µg CJCV2		Vac 1 (Day 4)	Day 4		Induration/Edema	None (0 mm)
10 µg CJCV2+ALFQ		Vac 1 (Day 5)	Day 5		Induration/Edema (measurement)	Mild (X mm)
		Vac 1 (Day 6)	Day 6		Pain	Moderate (X mm)
		Vac 1 (Day 7)	Day 7		Tenderness	Severe (X mm)
		Vac 1 (Day 8)	Day 8			
		Vac 1 (Day 9 – Day X)	Day 9 – Day X			
		Vac 2 (Day 29)	Post Vac			
		Vac 2 (Day 29)	Day 1			
		Vac 2 (Day 30)	Day 2			
		Vac 2 (Day 31)	Day 3			

Treatment Group	Participant ID	Vaccination Number (Study Day)	Day Relative to Vaccination	Assessment a	Symptom	Severity
		Vac 2 (Day 32)	Day 4			
		...	...			

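### As the SAP is written, millimetre size classes relabelled Mild/Moderate/Severe enter the any-local and any-solicited severity composites, and no planned display gives those composites on functional grades (minor)

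*SAP*

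**What the plan says.** Protocol 7.1.2 assesses ecchymosis, erythema and induration/edema on two scales. Table 3 is functional: Grades 1 to 3, according to whether the reaction does not interfere with, interferes with or prevents daily activity. Table 4 is by size: Small (<20 mm), Medium (20-50 mm) and Large (>50 mm), with no grade numbers.

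SAP 4.5.1 (Adverse Events) says that the size classes "will be presented as 'Mild', 'Moderate', and 'Severe' respectively for consistency with other AEs". It then lists, as solicited local events, five qualitative items (pain, tenderness, ecchymosis, erythema, induration/edema) and also "quantitative measurements of ecchymosis, erythema, and induration/edema".

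SAP 9.3.1 plans severity summaries for individual symptoms and for composites: "any local symptom, and any solicited symptom, the number and percentage of participants reporting the symptom will be summarized by severity". These are Tables 35-46. The any-local composite is also plotted in Figures 36-39. A footnote to Table 35 explains that the Maximum row "is the maximum severity reported within 7 days following vaccination". The measurement rows sit among the local symptoms, under the same None/Mild/Moderate/Severe columns.

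Two other sets of displays carry a solicited composite, both without severity. Table 30 has the row "At least one local solicited adverse event", and Tables 32-34 give occurrence only.

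**The concern.** The primary objective is the safety of CJCV2 with and without ALFQ, and the composites are the summary severity rows by arm. SAP Table 5 heads its functional columns Mild (Grade 1), Moderate (Grade 2) and Severe (Grade 3), so a reader will take Severe in a composite to mean Grade 3. If size classes feed the composite, some of those Severe counts may be large but functionally trivial reactions, and the row does not say so. The Grade 3 solicited criterion in the halting rules (Protocol 7.6.1 to 7.6.3) leaves size out, so the composite and that criterion would use the same word for different things. Figures 36-39 show only the any-local composite, so a reader of those figures alone cannot separate the two.

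**Working it through.** **1. The plan's own precision figure.** SAP section 5 gives 0-31% as the exact 95% interval for 0 events in 10 participants. The Clopper-Pearson upper limit is 1 − 0.025^(1/10) = 0.3085, so the figure reproduces.

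**2. What enters the composite.** SAP 4.5.1 gives 5 functional local items plus 3 measurement items, 8 in all. SAP 9.3.1, the Table 35 implementation note and the Table 35 footnotes contain no exclusion. A programmer taking the maximum over the listed local items would use all 8. For any solicited symptom, the systemic items and fever are added to these 8.

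**3. One participant followed through.** Take erythema over 50 mm that does not interfere with daily activity, with nothing else above Grade 1.
- Erythema row: Mild (Table 3, Grade 1).
- Erythema (measurement) row: Severe (Large, relabelled).
- Any-local and any-solicited maximum: Severe.
- The same composite on functional grades: Mild.

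With a 20-50 mm reaction the composite reads Moderate instead of Mild.

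**4. Size of the shift.** Call a participant size-only if over 50 mm on measurement with no Grade 3 item feeding the composite. With 10 per arm:
- 1 size-only participant: 1/10 = 10% (95% CI 0.3-44.5%) against 0/10 (0-30.8%).
- 2 size-only participants: 2/10 = 20% (2.5-55.6%) against 0/10.

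The documents give no probability p of being size-only. Under assumed values, the chance of at least one in an arm is 1 − (1 − p)^10: 18% at p = 0.02, 40% at 0.05, 65% at 0.10 and 89% at 0.20. Protocol 3.1.2 describes ALFQ local reactions in the malaria vaccine studies as mainly mild, short-lived tenderness. That points to the low end, but it reports no sizes and concerns other antigens.

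**5. Can a reader recover the functional composite?** From Listings 9 and 10, yes: functional and measurement results are listed per participant, and in Listing 10 the Severity "column for quantitative measurements should include the measurement in parentheses after the result". From the printed Maximum rows, the number with a functional local Grade 3 is bounded by
- lower = max(largest functional row, any-local − sum of measurement rows)
- upper = min(sum of functional rows, any-local).

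Example A, Severe counts: Pain 1, Tenderness 1, Erythema (measurement) 1, any-local 2. Lower = max(1, 2 − 1) = 1; upper = min(2, 2) = 2. Both are attainable. Pain and tenderness in one person, with a size-only reaction in another, gives 1. Pain and tenderness in two people, one of whom also has >50 mm erythema, gives 2. The functional rate is 10% or 20%, and the table cannot say which.

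Example B: Pain 2, Tenderness 1, Erythema (measurement) 1, any-local 2. Lower = max(2, 2 − 1) = 2; upper = min(3, 2) = 2. The count is exact.

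The count is therefore exact whenever the bounds meet, for example when the largest functional row equals the any-local row.

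**The case against.** The SAP discloses the relabelling and gives its reason. It lists the measurements as solicited local events and takes each participant's maximum. A worst-of-all-items composite follows from those rules and is conservative for a first-in-human trial, because it cannot hide a functional Grade 3. Protocol 7.1.2 presents Table 4 among its grading scales, so size is a recognised assessment. Protocol 9.4.2 asks that "maximum severity for each solicited AE will be determined for each subject and reported by study arm", and Tables 35-46 do this with functional and measurement rows kept apart. For any local symptom and any symptom it asks for the proportion reporting at least one event, which Tables 32-34 supply. In an arm of 10, a reader can often trace a Severe composite count to its source rows.

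Much of this stands. It is a good reason not to require that the composite be replaced, and the occurrence rows should hardly change, because a visible reaction normally has at least functional Grade 1. The reason given in SAP 4.5.1, however, concerns the labels on measurement results. It does not address pooling them with functional grades, and no footnote warns the reader that the pooled row is not a Grade 1-3 summary.

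A reader might infer that the SAP expressly pools the two scales, or that it breaches the protocol by doing so. Neither is supported. Pooling is inferred from the definitions and the absence of an exclusion, and the protocol's request for severity by individual event is met.

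**Conclusion.** The point holds as a minor matter of reporting clarity. As written, size classes enter the any-local and any-solicited severity composites in Tables 35-46 and the any-local composite in Figures 36-39, and no planned display gives either composite on functional grades. Each size-only participant adds 10 percentage points to an arm's Severe rate. That figure assumes 10 evaluable participants per arm and inclusion of the measurement items. The frequency is unknown and probably low.

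Two stronger conclusions might be drawn and should not be. One is that functional Grade 3 reactions go unreported or cannot be recovered: they appear symptom by symptom, the composites can be rebuilt from Listings 9 and 10, and the Maximum rows sometimes fix the local count exactly. The other is that participant protection or dose escalation is affected: the halting rules already exclude size, and no dosing decision rests on these final tables.

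**What to change.** In Tables 35-46, keep the current composite rows and add one functional-grade-only composite row each for any local symptom and any solicited symptom. The local one uses the Protocol Table 3 grades of pain, tenderness, ecchymosis, erythema and induration/edema. The any-solicited one adds the systemic and fever grades. State the derivation of both versions in SAP 9.3.1 and in a table footnote.

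In Figures 36-39, either plot the functional-only composite as well or footnote that the bars include millimetre size class. Footnote the measurement rows: size class, not Grade 1-3. The Mild/Moderate/Severe labels can stay.

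The cost is two added composites in each of 12 tables (2 × 12 = 24), a filter in the derivation, and the footnotes. No new data are needed. Because the existing composite is kept, a large reaction without functional impact still raises it. The only downside is slightly longer tables.
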